Clinical laboratory data will be summarized by the type of laboratory test. The frequency and percentage of subjects who experience abnormal clinical laboratory results (i.e. outside reference ranges) and/or clinically significant abnormalities will be presented for each measurement.

	Base	eline ¹	Treatment Extension ² Year 1				Treatment Extension ² Years 2-7			Early- Term/End of Study ³	Safety Follow-up (30-35 days) ¹³
Month	0	0.5	3	6	9	12	15, 21, 27, 33, 39, 45, 51, 57, 63, 69, 75, 81	18, 30, 42, 54, 66, 78	24, 36, 48, 60, 72, 84		
Түре	Clinic	Phone	Phone	Clinic	Phone	Clinic	Phone	Clinic	Clinic	Clinic	Phone
Informed Consent ¹	X										
Medical & Triheptanoin Treatment History ⁴	Х										
Growth ⁵	X			X		Х		Х	Х	Х	
SF10/12	X			X		Х		Х	Х	Х	
Echocardiogram (ECHO) ⁶	X					X			X	Х	
LC-FAOD Major Events Assessment ⁷	X	Х	X	X	X	X	Х	Х	X	Х	
LC-FAOD Biomarkers & Laboratory Measures ⁸	X			X		X		X	X	Х	
Vital Signs ⁹	X			Х		Х		Х	X	Х	
Physical Examination	X			Х		Х		Х	Х	Х	
Clinical Laboratory Tests ¹⁰	X			Х		Х		Х	X	Х	
Urine Pregnancy Test	X			Х		Х		Х	X	Х	
Adverse Events	Х	Х	Х	Х	Х	Х	Х	Х	Х	Х	X
Concomitant Medications	Х	Х	Х	X	Х	Х	Х	X	X	Х	Х

Table 2.1: Schedule of Events

	Baseline ¹		Treatment Extension ² Year 1			Treatment Extension ² Years 2-7			Early- Term/End of Study ³	Safety Follow-up (30-35 days) ¹³	
Month	0	0.5	3	6	9	12	15, 21, 27, 33, 39, 45, 51, 57, 63, 69, 75, 81	18, 30, 42, 54, 66, 78	24, 36, 48, 60, 72, 84		
Түре	Clinic	Phone	Phone	Clinic	Phone	Clinic	Phone	Clinic	Clinic	Clinic	Phone
Dietary Assessment and Diet diary ¹¹				Х		Х		Х	Х	Х	
UX007 Treatment & Compliance ¹²	X	Х	Х	X	X	X	Х	Х	X ¹²	X ¹²	
Plasma UX007 and Metabolites ¹⁴				X ¹⁴		X ¹⁴		X ¹⁴	X ¹⁴		
Standardized Meal ¹⁴				X ¹⁴		X ¹⁴		X ¹⁴	X ¹⁴		

¹ The Baseline visit may occur in conjunction with the last scheduled visit from study UX007-CL201. Assessments conducted at the last UX007-CL201 visit will be used for Baseline data to avoid duplication. Minor subjects who turn 18, should provide consent at their next visit.

² Clinic Visits will occur at 6 month intervals (± 2 weeks). The window for phone visits is ± 1 week.

³ Early Termination Visit should take place within 4 weeks of treatment discontinuation, if possible. The End of Study Visit will take place following commercial availability of UX007 in any region; if the End of Study Visit occurs within 2 weeks of a previous clinic visit, only the following assessments will occur: growth, vital signs, physical examination, urine pregnancy testing, AEs, concomitant medications, and UX007 compliance.

⁴ Medical history including major medical illness, diagnoses and surgeries will be collected for all subjects not previously enrolled in UX007-CL201. LC-FAOD maintenance treatment history, including triheptanoin treatment history, and relevant concomitant medications will be recorded (start date, stop date, dose, dose regimen). Any available sibling history of LC-FAOD will be noted.

⁵ Growth measurements include height and weight for all subjects, as well as head circumference for subjects aged \leq 36 months.

- ⁶ ECHO will be performed at Baseline and annually thereafter at indicated clinic visits (or if performed as routine care within 30 days prior to the Baseline or indicated clinic visits) or Early Termination if not performed within 6 months prior to termination. Additional tests may be performed during Treatment Extension Period if any abnormalities are detected or if medically indicated.
- ⁷ Major LC-FAOD events include skeletal myopathy (rhabdomyolysis), hepatic (hypoglycemia) and cardiac disease (cardiomyopathy) events, and are defined as any visit to the ER/acute care, hospitalization, emergency intervention (ie any unscheduled administration of therapeutics at home or in the clinic), or any similar event whether caused primarily by LC-FAOD or by an intercurrent illness complicated by LC-FAOD. The event type, levels of relevant laboratory parameters (including CK, glucose, and BNP/troponin), the number of days hospitalized and days in ICU, and the type and number of days of treatment and intervention will be recorded.

- ⁸ Biomarkers of clinical manifestations include skeletal myopathy (CK) and hepatic disease (fasting serum glucose and liver enzymes [ALT, AST, GGT]). Laboratory measures of LC-FAOD disease activity include total and free plasma carnitine, plasma acylcarnitines, and urine organic acids.
- ⁹ Vital sign measurements consist of seated systolic/diastolic BP measured in millimeters of mercury (mm Hg), HR (beats per minute), respiration rate (breaths per minute), and temperature in degrees Celsius (°C). Obtain at the beginning of each visit before any additional assessments are completed.
- ¹⁰ Clinical Laboratory Tests include standard serum chemistry, hematology, and urinalysis. These panels may overlap with LC-FAOD-specific biomarkers (including glucose and liver enzymes) which are called out separately in the table.
- ¹¹ Subjects and/or caregivers are required to maintain record of daily diet in a diary for 3 days prior to each clinic visit after consenting to participate in the trial. The daily diet should be representative of typical consumption for the subject. The diet diary will be reviewed with the site staff upon each indicated visit.
- ¹² Treatment with UX007 will begin after any necessary washout period for prohibited medications. UX007 dosing will be targeted at 25-35% of total caloric intake. If a subject has been receiving a lower dose, the individual may be titrated to a UX007 dose up to 25-35% of total caloric intake, while ensuring tolerability. However, a subject may remain at a lower dose if higher doses are not tolerated or at a higher dose at the discretion of the Investigator. UX007 will not be dispensed at the Month 84 (end-of-treatment visit), End of Study, Early Termination visits (as applicable).
- ¹³ Safety Follow-up Phone Call to be conducted 30-35 days after last dose of investigational study drug. Following commercial availability of UX007, a Safety Follow-up Phone Call will be conducted 30-35 days after last dose of investigational study drug for subjects not immediately continuing UX007 through another mechanism (ie, commercial product, IST, or compassionate use). The site personnel will initiate this safety follow-up telephone call to collect information on any ongoing or new AEs, serious adverse events (SAEs), and concomitant medications, as appropriate. Appropriate follow-up should continue until all safety concerns, in the Investigator's opinion, are resolved.
- ¹⁴ PK measurements will occur at select sites in a subset of subjects at two consecutively scheduled clinic visits (eg Month 18 and Month 24), excluding the Baseline Visit. Participating subjects (minimum of 12 subjects) will be fed a standardized meal containing one of their divided daily doses of UX007. Blood for plasma UX007 and metabolites will be collected pre-dose (within 15 minutes prior to start of meal) and at 30, 90, 120, and 240 minutes [± 5 minutes] after finishing the meal. For each sample collection, the meal start/stop times, calories consumed, UX007 dosing, and sampling times will be recorded.

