7.3.3 Removal of Subjects from Therapy or Assessment

In accordance with the Declaration of Helsinki, subjects have the right to withdraw from the study at any time for any reason. The Principal Investigator and Ultragenyx also have the right to remove subjects from the study. Ultragenyx must be notified of all subject withdrawals as soon as possible. Ultragenyx also reserves the right to discontinue the study at any time for either clinical or administrative reasons and to discontinue participation of an individual subject or Investigator due to poor enrollment or noncompliance, as applicable.

Subjects may be removed from the study for the following reasons:

- Occurrence of an unacceptable adverse event (AE)
- An illness that, in the judgment of the Principal Investigator or Ultragenyx, might place the subject at risk or invalidate the study
- At the request of the subject, Investigator, or Ultragenyx, for administrative or other reasons
- Protocol deviation or unreliable behavior

If the reason for removal of a subject from the study is an AE, the AE and any related test or procedure results will be recorded in the source documents and transcribed onto the Case Report Form (CRF). Each clinically significant abnormal laboratory value or other clinically meaningful abnormality should be followed until the abnormality resolves or until a decision is made that it is not likely to resolve. If such abnormalities do not return to normal within 30 days after the last dose given, their etiology should be identified and Ultragenyx should be notified. All unscheduled tests must be reported to Ultragenyx immediately.

If a subject discontinues from the study prematurely, every reasonable effort should be made to perform the Early Termination Visit procedures within four weeks of discontinuation. A Safety Follow-up Phone Call will be conducted 30-35 days after last dose of investigational study drug, even if the Early Termination Visit does not occur.

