5.10.1 Study Period 1 (Main Study Period)

Study period 1, or the main study period, starts from study day 1 till the last visit day in CL202. The last visit date is the last date among the early termination visit date, the study completion visit date, the safety follow up visit date, or the last visit date as of a clinical cutoff date, if applicable. Study period 1 will be used for all efficacy on FAS and safety analyses unless otherwise specified.

5.10.2 Study Period 2

Study period 2 has the same ending date as Study period 1 but starts from UX007 treatment day 1. Study period 2 will be used in select analyses for UX007-CL201 rollover subjects.

[figure not shown]
5.10.3 Study Period 3

Study period 3 starts from the 18 months (548 days) preceding UX007 treatment day 1 and ends 1 day prior to UX007 treatment Day 1. Study Period 3 is referred as the retrospective period for MCE data collection.

Study period 3 will be used for UX007-CL201 rollover subjects and UX007/trihep naïve subjects only in select analyses.

The following figure illustrates the definitions of the three study periods.

Figure 5.10.3.1: Diagram of Study Periods in CL202

Study Period 1 is defined for all enrolled subjects in CL202; Study Period 2 is defined for CL201 rollover subjects only; Study Period 3 is defined for CL201 rollover subjects and UX007/trihep naïve subjects. CL201 treatment period exists for CL201 subjects only;

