5.11 Annualized Event Rate

The numbers of MCE will be annualized for each subject using the following formula:

$$\text{Annualized Event Rate} = \frac{\text{Number of events}}{\text{Duration of data collection period in days}/365.25}$$

The number of MCEs will be derived as the total number of events as recorded in the major clinical event CRF that occurred during the specific data collection period. Whenever an annualized rate is calculated over study period 1, the number of days is calculated from study day 1 till the data cutoff date or the early termination/study completion visit date for subjects who have early terminated/completed the study.

Annualized event rates will be calculated for MCEs overall and for each event type (ie., rhabdomyolysis, hypoglycemia, and cardiomyopathy respectively).

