7.2.4 Missing Data for Efficacy Endpoints

For efficacy endpoints based on the duration of study period, the date of the study exit needs to be available. In case it is missing, the study period will end at the date of last assessment.

When a change from baseline is assessed, missing data will not be imputed and only subjects with a baseline and at least one post-baseline measurement will be included in the analysis.

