11.5 Schedule of Events

Table 11.5.1: Schedule of Events

MONTH	Baseline ¹		Treatment Extension ² Year 1				Treatment Extension ² Years 2-7			Early-Term/End of Study ³	Safety Follow-up (30-35 days) ¹³
	0	0.5	3	6	9	12	15, 21, 27, 33, 39, 45, 51, 57, 63, 69, 75, 81	18, 30, 42, 54, 66, 78	24, 36, 48, 60, 72, 84		
TYPE	Clinic	Phone	Phone	Clinic	Phone	Clinic	Phone	Clinic	Clinic	Clinic	Phone
Informed Consent ¹	X										
Medical & Triheptanoin Treatment History ⁴	X										
Growth ⁵	X			X		X		X	X	X	
SF10/12	X			X		X		X	X	X	
Echocardiogram (ECHO) ⁶	X					X			X	X	
LC-FAOD Major Events Assessment ⁷	X	X	X	X	X	X	X	X	X	X	
LC-FAOD Biomarkers & Laboratory Measures ⁸	X			X		X		X	X	X	
Vital Signs ⁹	X			X		X		X	X	X	
Physical Examination	X			X		X		X	X	X	
Clinical Laboratory Tests ¹⁰	X			X		X		X	X	X	
Urine Pregnancy Test	X			X		X		X	X	X	
Adverse Events	X	X	X	X	X	X	X	X	X	X	X

Concomitant Medications	X	X	X	X	X	X	X	X	X	X	X
Dietary Assessment and Diet diary ¹¹				X		X		X	X	X	
UX007 Treatment & Compliance ¹²	X	X	X	X	X	X	X	X	X ¹²	X ¹²	
Plasma UX007 and Metabolites ¹⁴				X ¹⁴		X ¹⁴		X ¹⁴	X ¹⁴		
Standardized Meal ¹⁴				X ¹⁴		X ¹⁴		X ¹⁴	X ¹⁴		

The Baseline visit may occur in conjunction with the last scheduled visit from study UX007-CL201. Assessments conducted at the last UX007-CL201 visit will be used for Baseline data to avoid duplication. Minor subjects who turn 18, should provide consent at their next visit.

Clinic Visits will occur at 6 month intervals (\pm 2 weeks). The window for phone visits is \pm 1 week.

Early Termination Visit should take place within 4 weeks of treatment discontinuation, if possible. The End of Study Visit will take place following commercial availability of UX007 in any region; if the End of Study Visit occurs within 2 weeks of a previous clinic visit, only the following assessments will occur: growth, vital signs, physical examination, urine pregnancy testing, AEs, concomitant medications, and UX007 compliance.

Medical history including major medical illness, diagnoses and surgeries will be collected for all subjects not previously enrolled in UX007-CL201. LCFAOD maintenance treatment history, including triheptanoin treatment history, and relevant concomitant medications will be recorded (start date, stop date, dose, dose regimen). Any available sibling history of LC-FAOD will be noted.

Growth measurements include height and weight for all subjects, as well as head circumference for subjects aged \leq 36 months.

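### Two exit contacts omit the major clinical event question, and the SAP has three unreconciled rules for where counted follow-up ends

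*Protocol*

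**What the plan says.** **Abbreviated End of Study Visit.** When UX007 becomes commercially available, each subject returns for an End of Study Visit, recorded as study completion (protocol 7.1). Footnote 3 to protocol Table 2.1 shortens it in one case: "if the End of Study Visit occurs within 2 weeks of a previous clinic visit, only the following assessments will occur: growth, vital signs". The list goes on to physical exam, pregnancy test, adverse events, concurrent drugs and compliance, and ends there. SAP Table 11.5.1 repeats the rule ("if the End of Study Visit occurs within 2 weeks of a previous clinic visit, only the following assessments will occur"). In the table itself, the row "LC-FAOD Major Events Assessment" is marked at every clinic and phone visit and in the Early Termination/End of Study column. SAP section 3 says MCEs are captured at each visit, clinic or phone, through early termination.

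**Safety Follow-up call.** The MCE row is blank for this call. Footnote 13 gives its purpose as "to collect information on any ongoing or new AEs, serious adverse events (SAEs), and concomitant medications, as appropriate". Protocol 7.3.3 requires it "30-35 days after last dose of investigational study drug, even if the Early Termination Visit does not occur", so for some subjects it is the only exit contact.

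**Counting rules.**
- SAP 5.11, numerator: "The number of MCEs will be derived as the total number of events as recorded in the major clinical event CRF".
- SAP 5.11, denominator over study period 1: study day 1 to the data cutoff, or to the early termination or study completion visit. The call is not named.
- SAP 5.10.1, end of study period 1: "The last visit date is the last date among the early termination visit date, the study completion visit date, the safety follow up visit date". This rule also allows for a clinical cutoff.
- SAP 7.2.4, when the exit date is unavailable: "In case it is missing, the study period will end at the date of last assessment".
- SAP 8.5.1: the primary rate is calculated over the whole of study period 1 and by 18-month interval.

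**The concern.** An annualized rate is sound only if events are looked for throughout the days in its denominator. Here the days can extend past the last occasion on which anyone was scheduled to ask about MCEs. On the abbreviated visit this follows directly from footnote 3 and SAP 5.11. For a subject with no Early Termination Visit it depends on which SAP rule governs.

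The error has one direction: days without ascertainment lower the on-treatment rate. That rate is the primary endpoint, and in the treatment-naïve and CL201-rollover cohorts it is also set against the pre-treatment rate. Adverse event questions at the same contacts fill the gap only in part. The numerator reads the MCE form alone, and neither document says how an MCE learned of through AE or SAE reporting reaches that form.

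**Working it through.** The documents give no figure for this point, so there is none to reproduce. The primary analysis is descriptive, so power and type I error do not enter.

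**Formula.** Let T be the days covered by MCE assessments and g the further days counted without one. At a constant event rate, the subject's rate is understated by g / (T + g). Values of T used: 183, 548 and 2557 days (Months 6, 18 and 84 in SAP Table 11.4.1).

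**Abbreviated End of Study Visit, g up to 14 days.**
- T = 183: 14/197 = 7.1%
- T = 548: 14/562 = 2.5%
- T = 2557: 14/2571 = 0.5%

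For the cohort, assume that commercial availability falls at random relative to the 6-monthly clinic visits. The chance of landing in the 2-week window is 14/182.6 = 7.7%, with a mean gap of 7 days. The average effect at T = 548 is 0.077 × 7/548, about 0.1%.

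**No Early Termination Visit, follow-up closed at the call.**
- Smallest g: last MCE contact on the day of the last dose, call 30 days later, so g = 30.
- Largest nominal g: contacts are 3 months apart and the call comes up to 35 days after the last dose, so g = 3 × 30.4375 + 35 = 126. Adding the visit windows (1 week phone, 2 weeks clinic) gives 147.

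| T (days) | g = 30 | g = 126 |
|---|---|---|
| 183 | 30/213 = 14% | 126/309 = 41% |
| 548 | 30/578 = 5.2% | 126/674 = 19% |
| 2557 | 30/2587 = 1.2% | 126/2683 = 4.7% |

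**Early Termination or full End of Study Visit attended, call made afterwards.** Under SAP 5.11, g = 0. If study period 1 under 5.10.1 governs instead, and the last dose is taken on the visit day, g = 30 to 35. At T = 548 that is 30/578 = 5.2% to 35/583 = 6.0%.

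**Scale in events (assumption).** The chart review in protocol 5.2.3 reports 319 hospitalizations over 241 years, or 1.32 per year, pooled before and after treatment. It is not an MCE rate and serves only as a scale. At that rate the expected number of events in the gap is 14/365.25 × 1.32 = 0.05 for the abbreviated visit, and 0.11 (g = 30) to 0.46 (g = 126) for the call.

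**Interval summary.** An abbreviated visit soon after Month 18 or Month 36 opens a new 18-month interval of at most 14 days with no scheduled MCE question. SAP 8.5.1 sets no minimum interval length.

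**The case against.** The strongest case against the point has four parts.

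- **SAP 5.11 is the specific rule for the rate and does not name the call.** SAP 8.5.4.1 and 8.5.5.1 likewise close the pre/post event count at the termination visit. This stands. A reader might infer that every subject's counted follow-up runs to the call; the documents do not support that. Days reach the call only if 5.10.1 is taken to govern, or under 7.2.4 when no exit date is recorded. Skipping the visit need not leave that date missing, and the last assessment in 7.2.4 could mean the last efficacy assessment. What remains is an unreconciled definition.
- **The event that led to stopping is not lost.** A reader might infer that it is, because protocol 7.3.3.1 makes a changed or more frequent major event a prompt to consider discontinuation. But the investigator must already know of that event to make the decision, 7.5.2.3 has it reported as an AE, and 7.3.3 has an AE that causes removal entered in the case report form. Nothing limits MCE form entries to scheduled assessments. So the claim of selective loss among subjects who did badly fails.
- **AEs and SAEs are asked about at both contacts, and hospitalised MCEs are SAEs.** This stands, so events may be missed rather than are missed. Those exposed are chiefly emergency visits and unplanned home treatment in the subject's usual pattern.
- **Large individual figures need stacked conditions.** With the last MCE contact at Month 9 (day 274), last dose on day 360 and the call on day 393, one gets 119/393 = 30%. But day 360 lies inside the Month 12 window (351 to 379), so that subject must miss both Month 12 and Early Termination and also be closed at the call.

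None of this removes the conflict between footnote 3 and SAP section 3, or the lack of one agreed end date for a subject without an exit visit.

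**Conclusion.** The point holds as a correctable gap of limited size. On the abbreviated End of Study Visit, up to 14 days are counted without an MCE question, which is a very small effect across the cohort. For a subject who stops without an Early Termination Visit, the size depends on an end date that the SAP leaves unsettled. If it is the call, 5% to 19% of that subject's rate at 548 days is exposed, more with shorter follow-up and less with longer. These are upper bounds: they assume a constant event rate and that no MCE in the gap reaches the MCE form by another path.

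The documents do not say how many subjects take either route, so no cohort figure can be given for the second. The ordinary Early Termination Visit and the full End of Study Visit do assess MCEs and are not affected under SAP 5.11. The 18-month comparison in treatment-naïve subjects is touched only for those who leave before 18 months.

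**What to change.** 1. Add the Major Events Assessment to the abbreviated list in footnote 3 of protocol Table 2.1 and in SAP Table 11.5.1.
2. At the Safety Follow-up call, when no Early Termination Visit took place, ask about MCEs since the last contact, with dates, and enter them on the MCE form.
3. Align SAP 5.10.1, 5.11 and 7.2.4 so that the event count and the day count share one end date. That date is the early termination or completion visit, as 5.11 has it. Without such a visit, it is the last date up to which MCE status was ascertained, and no later than the last dose. The cap matters: ending at the call itself would add 30 to 35 off-treatment days to the rate.
4. State how an MCE identified through AE or SAE reporting is entered on the MCE form.

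The cost is two schedule entries and a short SAP clarification. The question is already asked at every other phone contact, so it adds minutes to contacts that take place anyway. Where contacts have already been held without the question, the SAP change alone deals with the denominator: end both counts at the last date on which MCE status was ascertained, which for an abbreviated visit is the preceding clinic visit.

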4 LIST OF ABBREVIATIONS AND DEFINITION OF TERMS

Abbreviations

AE	adverse event
ALT	alanine aminotransferase
APBD	adult polyglucosan body disease
AST	aspartate aminotransferase
ATP	adenosine triphosphate
BNP	B-type natriuretic peptide
BP	blood pressure
BUN	blood urea nitrogen
CACT	carnitine-acylcarnitine translocase
CFR	Code of Federal Regulations
CK	creatine kinase
CPT	carnitine palmitoyltransferase
CRF	Case Report Form
ECHO	echocardiogram
EC	Ethics Committee
EDC	electronic data capture
EF	ejection fraction
ER	emergency department/room
EudraCT	European Union Drug Regulating Authorities Clinical Trials
FAOD	fatty acid oxidation disorders
FDA	Food and Drug Administration
GCP	Good Clinical Practice
GGT	gamma glutamyl transpeptidase
GMP	Good Manufacturing Practice
GSD II	glycogen storage disease type II
HDPE	high-density polyethylene
HIPAA	Health Insurance Portability and Accountability Act
HR	heart rate
IB	Investigator's Brochure
ICF	Informed Consent Form
ICH	International Conference on Harmonisation of Technical Requirements for Registration of Pharmaceuticals for Human Use
ICU	intensive care unit
IND	Investigational New Drug (application)
IRB	Institutional Review Board
нъ	
IUD	intrauterine device

IUS	intrauterine system
LC-FAOD	long-chain fatty acid oxidation disorders
LCHAD	L-3-hydroxy-Acyl-CoA dehydrogenase
LDH	lactate dehydrogenase
MADD	multiple acyl-CoA dehydrogenase deficiency
MCAD	medium-chain acyl-CoA dehydrogenase deficiency
MCH	mean corpuscular hemoglobin
MCHC	mean corpuscular hemoglobin concentration
MCS	Mental Component Summary
MCT	medium chain triglyceride
MCV	mean corpuscular volume
MedDRA	Medical Dictionary for Regulatory Activities
NADH	nicotinamide adenine dinucleotide hydrogen (reduced form)
NCI CTCAE	National Cancer Institute Common Terminology Criteria for Adverse Events
NOAEL	No observed adverse effect level
PCS	Physical Component Summary
РК	pharmacokinetic
PO	oral, by mouth
PT	Preferred Term
RBC	red blood cell
SAE	serious adverse event
SAP	Statistical Analysis Plan
SF	shortening fraction
SF-10	Medical Outcomes Study 10-Item Short Form for Children
SF-12	Medical Outcomes Study 12-Item Short Form
SOC	System Organ Class
SUSAR	suspected unexpected serious adverse reaction
TCA	tricarboxylic acid
TFP	trifunctional protein
US	United States
UX007	Investigational Product/study drug, triheptanoin
VLCAD	very long chain acyl-CoA dehydrogenase
WBC	white blood cell

Definition of Terms

Investigational Product is defined as, "A pharmaceutical form of an active ingredient or placebo being tested or used as a reference in a clinical trial, including a product with a marketing authorization when used or assembled (formulated or packaged) in a way different from the approved form, or when used for an unapproved indication, or when used to gain further information about an approved use" (from International Conference on Harmonisation of Technical Requirements for Registration of Pharmaceuticals for Human Use [ICH] Harmonised Tripartite Guideline E6: Guideline for Good Clinical Practice).

The terms "Investigational Product" and "study drug" may be used interchangeably in the protocol.

